### **6.3 SUBJECT SETS ANALYSED**

The following patient sets are defined in section 7.3 of the protocol:

- **Randomised set (RS)**  
This patient set includes all randomised patients, whether treated or not. Treatment will be evaluated as randomised.
- **Treated set (TS)**  
This patient set includes all patients who were dispensed study medication and were documented to have taken at least one dose of investigational treatment. Treatment will be evaluated as randomised.

In addition the following patient set is defined:

- **Screened Set (SCR)**  
Consists of all patients screened for the trial, with informed consent given and who completed at least one screening procedure at Visit 1.

For sensitivity analyses the following patients set is defined:

- **Sensitivity analysis set 1 (SensRS1)**  
Randomised patients excluding patients with an iPD related to 6MWT, i.e. iPD categories A2.14, G3.48 and G3.49 of [Table 6.2: 1](#)
- **Sensitivity analysis set 2 (SensRS2)**  
Randomised patients excluding patients for which at least one on-treatment value of urine glucose test result was included in the safety laboratory reports posted to a portal by the central laboratory, and the reports were accessed before database lock.
- **Sensitivity analysis set 3 (SensRS3)**  
Randomised patients excluding non-diabetic patients for which at least one on-treatment value of urine glucose test result was included in the reports posted and accessed before database lock.

Demographics and baseline characteristics as well as the efficacy analysis will be based on the RS. Demographics will be repeated on the TS if the number of patients in the analysis sets differ by more than 5%. The safety analysis will be based on the TS.

Overall number of patients participating in the study (screened, randomised, screened but not randomised, etc.) by region and country will be based on the SCR.

Table 6.3: 1 Subject sets analysed

Class of endpoint	Subject set		
	Screened Set	Randomised set	Treated set
Primary and key secondary endpoints		X	X
(other) Secondary and further endpoints		X	
Safety endpoints			X
Demographic/baseline endpoints		X	X 
Extent of exposure			X
Disposition	X		

 Demographics will be repeated on the TS if the number of patients in the analysis sets differ by more than 5%.

#### 6.4 SUBGROUPS

Subgroups are provided in [Table 6.4: 1](#). Missing categories for subgroup variables will not be considered in the respective analysis.

Subgroups with fewer than 14 patients in total (yielding approximately 7 patients per treatment group) will generally not be included in the analyses of subgroups. Small subgroups can be combined into other subgroups. Final decision will be made at final Blinded Report Planning Meeting (BRPM).

Although several subgroup analyses are prespecified in Table 6.4: 1, the subgroup analysis by Diabetes at baseline (diabetic, non-diabetic) is the medically and academically most important subgroup analysis.

Table 6.4: 1 Categories of covariates for displays of baseline characteristics and subgroup analyses

Variable	Categorisation	Demo-graphics 	Subgroups for Efficacy endpoints 	Safety
Age (years)	<50	X		
	50 to <65 65 to <75 75 to <85 ≥ 85			
	< 65 ≥65	X	X	
Sex	Male	X	X	
	Female			
Region 	Europe, Australia, North America	X		
	Europe or Australia North America		X	
Ethnicity	Hispanic/ Latino	X	X	
	Not Hispanic/ Latino			
Race	American Indian or Alaska Native	X		
	Asian			
	Black or African-American			
	Native Hawaiian or other Pacific Islander			
	White			
	White Black/ African-American Asian Other including mixed race		X	
BMI (kg/m  )	<30	X	X	
	≥30			
eGFR at baseline (mL/min/1.73m  )	≥90	X		
	60 to <90			
	45 to <60			
	30 to <45			
	20 to <30			
	<20			
		≥60 45 to <60 30 to <45 <30		X

Table 6.4: 1 Categories of covariates for displays of baseline characteristics and subgroup analyses (cont.)

Variable	Categorisation	Demo- graphics 	Subgroups for Efficacy endpoints 	Safety
Diabetes at baseline 	DM, pre-DM, non-DM (excl. pre-DM)	X		
	DM, non-DM		X	X (only hypoglycemia)
History of hypertension	Yes / No	X		
Baseline BP	SBP<140 and DBP<90 vs. SBP≥ 140 or DBP≥90	X	X	
Atrial Fibrillation at baseline 	Yes/ No	X	X	
Baseline LVEF	<20, >=20 to <=30, >30 to <=35, >35	X	X	
History of valvular disease	Yes / No	X		
Cause of HF	Ischemic Hypertensive Valvular heart disease Diabetic Alcoholism Idiopathic Cardiomyopathy Other	X		
Time since diagnosis of HF	≤ 1 year, >1 to ≤ 5 years, > 5 to ≤ 10years, > 10 years	X		
NYHA at baseline	I/II/III/IV	X		
	II  vs. III/IV		X	
NT-proBNP (separated by atrial fibrillation status) at baseline 	atrial fibrillation at baseline and < / ≥ median;		X	
	no atrial fibrillation at baseline and < / ≥ median			

Table 6.4: 1 Categories of covariates for displays of baseline characteristics and subgroup analyses (cont.)

Variable	Categorisation	Demo- graphics 	Subgroups for Efficacy endpoints 	Safety
Baseline KCCQ-TSS	By quartiles		X (only KCCQ-TSS and 6MWT)	
Baseline CHQ-SAS Dyspnea domain	By quartiles		X (only CHQ- SAS dyspnea and 6MWT)	
Baseline PGI-S Dyspnea	5 categories	X	X (only CHQ- SAS dyspnea)	
Baseline PGI-S HF symptoms	5 categories	X	X (only KCCQ-TSS)	
Baseline distance walked in 6 minutes	< / >= median		X (only 6MWT)	
Baseline use of ACE- inhibitor, ARB or ARNi	Yes / No	X 	X	
Baseline use of diuretics other than MRA	Yes / No	X 	X	
Baseline use of MRA	Yes / No	X 	X	
Baseline use of loop or high-ceiling diuretics	Yes / No	X 	X	
Baseline haemoglobin	< / >= median		X	

1 The column demographics shows categories displayed for overall demographics.

Demographics are not planned by subgroup.

2 Subgroups planned for the following endpoints: primary and key secondary endpoints.

3 Region categorisation: see [Table 9.1: 1](#).

4 Diabetes at baseline categorisation: see [Table 9.2: 1](#); for subgroup analysis ‘pre-DM’ and ‘non-DM (excluding pre-DM)’ will be combined into the category ‘non-DM’

5 atrial fibrillation at baseline means atrial fibrillation in last ECG before treatment intake

6 patients with NYHA class I are counted in subgroup NYHA class II

7 Median NT-proBNP will be calculated for randomised patients with/without atrial fibrillation at baseline separately and subgroups will be defined based on the respective median for patients with/without atrial fibrillation at baseline accordingly

8 part of the presentation of baseline concomitant therapy as outlined in [Section 7.2](#)

## 6.5 POOLING OF CENTRES

Not applicable because centre/country is not included in the statistical model.

## 6.6 HANDLING OF MISSING DATA AND OUTLIERS

The imputation strategy for all confirmatory analyses, i.e. primary analysis of primary and key secondary endpoints, will be based on the following principle:

Patients with an available week 12 measurement of the endpoint, regardless of whether on or off-treatment, will be ranked based on change from baseline at week 12. If a patient performs the visit but the 6MWT is not done this will not be regarded as missing data. This case will be evaluated as a measured distance of 0m.

All imputed data due to missing data will be lower than the measured values and will be ranked in the following orders: Patients who do not have a clinical event (death, serious adverse event or any AE leading to discontinuation) and have a value at week 6 are ranked by their values. Patients who do not have a clinical event and have no valid post-baseline value are ranked below. Patients who have a clinical event are given a lower rank and death is ranked below any other clinical event by time to death from randomisation.

A treatment-emergent SAE with outcome “recovered with sequelae” leading to an amputation is considered to be an ongoing clinical event.

Imputation will not be applied for any parametric analysis, descriptive statistics and derivation of responder thresholds for the key secondary endpoints.

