## 7.5 HANDLING OF MISSING DATA

Patients with an available week 12 measurement of the 6MWT, regardless of whether on or off-treatment, will be ranked based on change from baseline in 6MWT distance at week 12.

If a patient performs the visit at week 12 but is unable to walk or unable to perform the 6MWT due to safety concerns, then this will be noted accordingly in the case report form and will not be regarded as missing data. This case will be evaluated as a measured distance of 0m.

Missing data will be imputed according to the rules outlined in [table 7.5: 1](#), and ranks will be assigned based on the imputed data. Imputed data will also be used to calculate the Hodge Lehmann estimates for the median difference. Note that no imputation will be used in the MMRM analysis that serves as sensitivity analysis in this trial.

All imputed data due to missing data will be lower than measured values. The lowest measurable value of the primary endpoint of change from baseline in 6MWT distance is a reduction by 350m, i.e. the highest possible baseline value (350 m), and at week 12 the lowest possible value of 0m. Therefore, all imputed values for change from baseline for patients with missing walking distance at week 12 are below -350 m.

Table 7.5: 1 Imputation rules for missing primary endpoint

	Category	Ranking	Case description	Imputed change from baseline in 6MWT for described case (in m)*
1	Missing data on 6MWT at week 12 and no clinical event: Patients with missing 6MWT at week 12 and no event as in category 2 or 3	If post-baseline value is available, rank by last available value. Rank below if no post-baseline value is available	Patient has a change from baseline to last available value of x m, no clinical event	-352 +x/1000
			No information of post-baseline 6MWT distance and no clinical event	-354
2	Missing data and clinical event (except death). A clinical event is defined as ongoing SAE or AE leading to treatment discontinuation and patient is alive at week 12	Ranked above patients who died, but below patients with missing data and no clinical event.	Patient has ongoing SAE or AE leading to treatment discontinuation, no information of week 12 6MWT distance and patient alive at week 12.	-356
3	Patient died before the measurement of 6MWT at week 12 was conducted.	Ranked by time to death from randomization	Patient died y days after randomization	-358+y/1000

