### **3. INTRODUCTION**

*As per ICH E9 (1), the purpose of this document is to provide a more technical and detailed elaboration of the principal features of the analysis described in the protocol, and to include detailed procedures for executing the statistical analysis of the primary and secondary variables and other data.*

*This TSAP assumes familiarity with the Clinical Trial Protocol (CTP), including Protocol Amendments. In particular, the TSAP is based on the planned analysis specification as written in CTP Section 7 “Statistical Methods and Determination of Sample Size”. Therefore, TSAP readers may consult the CTP for more background information on the study, e.g., on study objectives, study design and population, treatments, definition of measurements and variables, planning of sample size, randomisation.”*

*SAS® Version 9.4 will be used for all analyses.*

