## **4. CHANGES IN THE PLANNED ANALYSIS OF THE STUDY**

### **4.1 CHANGES NEWLY INTRODUCED FROM THE CLINICAL TRIAL PROTOCOL**

Analyses of the following endpoints have been added:

- Systolic blood pressure
- Diastolic blood pressure
- Body weight

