### 6.6.1 Primary endpoint

Handling of missing data is described in section 7.5 of the clinical trial protocol for the primary analysis and subgroup analysis of the primary endpoint change from baseline in 6MWTD.

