##### Observed case including data after treatment discontinuation (OC-AD):

All available data are considered, including values obtained on treatment or post-treatment. Imputed records are not included.

Measurements are assigned to planned weeks according to [Table 6.7: 1](#) and [Table 6.7: 2](#)

Worst case imputation (WCI):

All available data as described for OC-AD and additionally including worst case imputation as described in [Sections 6.6.1 – 6.6.3](#). This imputation will only be considered in non-parametric analyses.

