## **7.4 PRIMARY ENDPOINT**

### **7.4.1 Primary analysis of the primary endpoint**

The primary endpoint ‘change from baseline to week 12 in exercise capacity’ as measured by the change from baseline to week 12 in distance walked in 6 minutes will be evaluated using a normal approximation of the Wilcoxon rank test using the randomised set.

For estimation of effect, non-parametric Hodges-Lehmann estimate for the median difference will be used. Corresponding 95% confidence intervals will be displayed. Any confirmatory conclusion such as for hierarchical testing will be based on the result of the Wilcoxon rank test and will not consider the Hodges-Lehmann estimate or the corresponding confidence interval, which are given to support interpretation.

If no 6MWT is available at week 12, an imputed value as defined in Section 7.5 of the CTP will be used.

The primary analysis will be conducted on all randomised patients, regardless of whether on or off-treatment on the day of 6MWT assessment. Where more than one measurement is available for the same day (duplicate measurements), the longest distance walked will be used for analysis. In case more than one 6MWT results in the same distance walked, the first assessment will be used for analysis.

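### SAP 6.6 restates the protocol's 0 m rule without its reason condition, so an attended week 12 visit with the walk test missed for any reason would score as a measured 0 m (minor; wrong as written)

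*SAP*

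**What the plan says.** **Protocol 7.5.** The 0 m score has a stated trigger: "If a patient performs the visit at week 12 but is unable to walk or unable to perform the 6MWT due to safety concerns". The same rule fixes how the case is documented and classed: "then this will be noted accordingly in the case report form and will not be regarded as missing data". Such a case counts as a walked distance of 0 m. All other missing week 12 distances are imputed from Table 7.5:1, below -350 m:

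- -352 + x/1000 with no clinical event and a last available change of x;
- -354 with no clinical event and no post-baseline value;
- -356 with an ongoing SAE or an AE leading to discontinuation;
- -358 + y/1000 for death on day y.

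**SAP 6.6.** The principle for the confirmatory analyses contains this sentence: "If a patient performs the visit but the 6MWT is not done this will not be regarded as missing data". The next sentence assigns a measured 0 m. No reason for the missed test and no CRF note are required.

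**Elsewhere in the SAP.** Section 6.6.1: "Handling of missing data is described in section 7.5 of the clinical trial protocol for the primary analysis". Section 7.4.1: "If no 6MWT is available at week 12, an imputed value as defined in Section 7.5 of the CTP will be used". Section 3: "the TSAP is based on the planned analysis specification as written in CTP Section 7". Section 4.1 lists changes from the protocol under "Analyses of the following endpoints have been added" and names only blood pressure and body weight. The history table (Section 10, revision of 21 October 2019) lists the handling of a week 12 visit without a 6MWT as a clarification and gives consistency with the protocol as the reason.

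**The concern.** The sentence decides which attended visits count as missing for the primary endpoint. The protocol separates a patient who could not walk, for whom 0 m is a meaningful result, from a patient whose test was not done for an unrelated reason such as refusal, lack of time or a site problem. SAP 6.6 merges the two. A programmer working from SAP 6.6 alone would give the second patient a non-missing value that ranks above every imputed case; one working from SAP 6.6.1 or 7.4.1 would impute from Table 7.5:1. No sentence in either document says which text prevails, and the history note tells the reader that there is nothing to reconcile.

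At stake are the reproducibility of the primary data set and, depending on coding, the analyses that use observed values without imputation: the OC-AD MMRM, the descriptive statistics and the responder analysis at 30 m or more.

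**Working it through.** **1. The two rules side by side, for an attended week 12 visit with the test missed for a reason other than inability or safety**

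| | Protocol 7.5 | SAP 6.6 read literally |
|---|---|---|
| Status | missing | not missing |
| Change scored | about -352, or -354, or -356 m | 0 minus baseline |
| Range | about -352 to -356 m | -100 to -350 m |
| Rank | among the imputed cases | above all imputed cases |

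The SAP range follows from the entry criteria (baseline 100 to 350 m). The gap runs from 352 - 350 = 2 m to 356 - 100 = 256 m.

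**2. The plan's own figures**

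Inputs from protocol 7.7: difference 30 m, SD 72 m, two-sided alpha 0.05, power 90%, 150 per group.

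- P(X<Y) = Φ(-30/(72√2)) = 0.384, as stated.
- n = (1.960 + 1.282)² / (6 × (P - 0.5)²) = 130.5 with P unrounded, so 131 per group, as stated.
- Simulated Wilcoxon power at 150 per group with 5%, 8% and 10% imputed to worst case is 89.9%, 87.6% and 85.9%. The protocol gives 90%, 87% and 85%.

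**3. Effect on the confirmatory test**

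The documents give no rate for tests missed at an attended visit for other reasons, so the counts below are assumptions. For scale, the protocol's allowance of about 5% for all drop-out and imputation is 0.05 × 150 = 7.5 patients per arm.

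Simulation: 8,000 runs per scenario, 150 per arm, change N(30, 72) against N(0, 72), baseline uniform on 100 to 350 m and independent of change, no other drop-outs. Wilcoxon normal approximation, power in favour of empagliflozin.

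| Misses, empagliflozin/placebo | Protocol rule | SAP 6.6 literal |
|---|---|---|
| 1/1 | 93.6% | 93.7% |
| 2/2 | 93.2% | 93.2% |
| 3/3 | 93.0% | 93.1% |
| 2/1 | 91.7% | 91.8% |

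The mean Hodges-Lehmann estimate at 3/3 is 29.93 m under both rules.

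The reason is simple. At a mean baseline of 225 m the literal score is -225 m. The chance of an observed placebo change below that is Φ(-225/72) = 0.0009, so the patient stays at the bottom of the ranks either way. Only a low baseline matters more: at 100 m, Φ(-100/72) = 0.08 of placebo changes would rank below.

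A deliberately extreme case scores every missing test as 0 m. It assumes a baseline of N(270, 60) limited to 100 to 350 m, with 20,000 runs. Power is then 90.2%, 87.5% and 84.8% at 5%, 8% and 10%, against 89.9%, 87.6% and 85.9% with imputation. The largest difference is 85.9 - 84.8 = 1.1 points, and its direction is not constant.

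**4. Conditional effect on mean-based and responder outputs**

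This applies only if these cases are coded as observed 0 m. Hand calculation at mean baseline 225 m with 2/1 misses:

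- Empagliflozin mean: (148 × 30 - 2 × 225)/150 = 26.6 m.
- Placebo mean: (149 × 0 - 225)/150 = -1.5 m.
- Difference: 26.6 + 1.5 = 28.1 m instead of 30 m.

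An ANCOVA on baseline, used as a stand-in for the MMRM without week 6 data, also gives 28.1 m. For 3/3 the hand figure is 29.4 m and the ANCOVA figure 29.5 m.

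Responders at 30 m or more: 50.0% against 1 - Φ(30/72) = 33.8%, a difference of 16.2 points if the cases are left missing. Kept as non-responders at 2/1: (148/150) × 50.0 - (149/150) × 33.8 = 15.7 points.

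**The case against.** The strongest defence is that SAP 6.6 is an introductory summary and the operative rule is settled elsewhere. Sections 6.6.1 and 7.4.1 send the primary endpoint to protocol 7.5. Worst case imputation is defined as "additionally including worst case imputation as described in" Sections 6.6.1 to 6.6.3, not the opening text of 6.6. Section 4.1 declares no change to this rule. The paragraph is shorthand in other respects too: it speaks of a serious adverse event and a week 6 value where Table 7.5:1 has an ongoing SAE and the last available value. The history note itself suggests that the authors meant to repeat the protocol. This stands as evidence of intent, and it makes the protocol rule the better-supported one. It does not make the sentence correct. Section 7.4.1 applies imputation when no 6MWT is available, while 6.6 declares these same cases not missing.

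A reader might infer three stronger points that the documents do not support:

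- **That the 0 m rule spreads to other visits, because the sentence names no week.** The sentence before it concerns week 12 measurements, and the history table describes the item as a week 12 matter.
- **That the SAP deliberately changed the primary analysis.** The cross-references and Section 4.1 point the other way.
- **That the MMRM is materially biased.** This needs the cases to be coded as observed. SAP 6.6 bars imputation in parametric and descriptive analyses. Section 6.6.4 excludes imputed records from OC-AD, and Sections 7.4.2 and 7.6 specify no imputation of missing values. Only the word measured leaves the coding open. How the protocol's own 0 m cases enter the MMRM is a separate question that arises under either text.

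**Conclusion.** Minor, and wrong as written. SAP 6.6 omits the reason and the CRF note that protocol 7.5 attaches to the 0 m score, and so contradicts the rule to which SAP 6.6.1 and 7.4.1 defer. The history table's statement of consistency with the protocol is wrong for this item; that follows from the same mismatch and is not a second defect.

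The text mismatch is certain. The effect on the confirmatory Wilcoxon test is negligible: 0.1 point of power or less in the small splits tabulated, and about 1 point even if every missing test up to 10% were scored 0 m. The Hodges-Lehmann estimate does not move at 3/3. Any visible shift elsewhere, such as 30 m to about 28 m at 2/1, rests on assumed counts, a simplified model and a coding that the SAP mostly argues against. It should be read as an illustration, not as an expected bias.

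**What to change.** 1. In SAP 6.6, replace the sentence with the protocol's condition (week 12 visit performed, patient unable to walk or unable to do the test for safety reasons, noted in the CRF), or with a plain cross-reference to protocol 7.5.
2. Add that every other week 12 6MWT not done is missing: Table 7.5:1 in the primary analysis, left missing in OC-AD analyses.
3. Correct the history-table note for this item.

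The cost is two SAP sentences and one note. The protocol already requires a CRF note for inability or safety concerns, so a not-done test without that note can be treated as missing, with no new data item. The CRF itself is not among the documents, so the presence of that field should be confirmed.

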### 6.6.1 Primary endpoint

Handling of missing data is described in section 7.5 of the clinical trial protocol for the primary analysis and subgroup analysis of the primary endpoint change from baseline in 6MWTD.

### 6.6.2 Key Secondary endpoint

Missing individual items within a questionnaire will be handled according to the rules in [Appendix 9.4](#).

Patients with an available week 12 measurement, regardless of whether on or off treatment, will be ranked based on change from baseline at week 12 regardless of clinical events.

For any missing week 12 assessment of the KCCQ-TSS, the below imputation will be applied for the primary analysis and subgroup analysis in accordance to the strategy for the primary endpoint:

Since the lowest possible value for change from baseline in KCCQ-TSS is 0 minus the highest possible baseline value (100), all imputed values for change from baseline are below -100 as described in [Table 6.6.2: 1](#) below.

Table 6.6.2: 1 Imputation Rules for missing KCCQ-TSS Assessments at Week 12

	Category	Ranking	Case description	(Imputed) Change from baseline in KCCQ-TSS for described case
1	Missing data on KCCQ-TSS at week 12 and no clinical event: Patients with missing KCCQ-TSS at week 12 and no event as in category 2 or 3	If post-baseline value is available, rank by last available value.	Patient has a change from baseline to last available value of x points, no clinical event	-102 +x/1000
		Rank below if no post-baseline score is available	No information of post-baseline KCCQ-TSS and no clinical event	-104
2	Missing data and clinical event (except death). A clinical event is defined as ongoing SAE at week 12 or AE leading to treatment discontinuation and patient is alive at week 12	Ranked above patients who died, but below patients with missing data and no clinical event.	Patient has ongoing SAE or AE leading to treatment discontinuation, no week 12 KCCQ-TSS assessment and patient alive at week 12.	-106
3	Patient died before the assessment of KCCQ-TSS at week 12 was conducted.	Ranked by time to death from randomisation	Patient died y days after randomisation	-108+y/1000

For any missing week 12 assessment of the CHQ-SAS, the below imputation will be applied for the primary analysis and subgroup analysis in accordance to the strategy for the primary endpoint:

Since the lowest possible value for change from baseline in CHQ-SAS dyspnea (fatigue) score is 1 minus the highest possible baseline value (7) all imputed values for change from baseline are below -6 as described below in [Table 6.6.2: 2](#).

Table 6.6.2: 2 Imputation Rules for missing CHQ-SAS Assessments at Week 12

	Category	Ranking	Case description	(Imputed) Change from baseline in CHQ-SAS for described case
1	Missing data on CHQ-SAS at week 12 and no clinical event: Patients with missing CHQ-SAS at week 12 and no event as in category 2 or 3	If post-baseline value is available, rank by last available value.	Patient has a change from baseline to last available value of x points, no clinical event	$-12 + x/1000$
		Rank below if no post-baseline score is available	No information of post-baseline CHQ and no clinical event	-14
2	Missing data and clinical event (except death). A clinical event is defined as ongoing SAE at week 12 or AE leading to treatment discontinuation and patient is alive at week 12	Ranked above patients who died, but below patients with missing data and no clinical event.	Patient has ongoing SAE or AE leading to treatment discontinuation, no week 12 CHQ assessment and patient alive at week 12.	-16
3	Patient died before the assessment of CHQ at week 12 was conducted.	Ranked by time to death from randomisation	Patient died y days after randomisation	$-18 + y/1000$

Missing change from baseline due to missing baseline questionnaire will not be imputed.

